1231 Participants will be recruited equally across the following groups (see sample size calculation section
 1232 also).

1233 **Table 10: Recruitment Table**

1234

1235

	Urgency with significant urgency incontinence	Urgency without significant urgency incontinence	Controls (without urgency or other LUTS)
Male	42	42	42
Female	42	42	42

1236 Half of the participants will be males, and the other half will be females. In general, neuroimaging data
 1237 and sensory testing data cannot be compared across sex. Within each sex, the three groups will be age-
 1238 matched also, as age can be a confounding factor for the neuroimaging studies (e.g. white matter
 1239 hyperintensities caused by chronic vascular conditions in older subjects may complicate DTI
 1240 interpretation) and for sensory pain testing. To control for the effects of age, recruitment will be age-
 1241 stratified (i.e., less than 60 years old, 60 years old and older) to prevent a skewed age distribution. We
 1242 anticipate that men with incontinence or women without incontinence will take longer to recruit
 1243 compared to the other groups in each sex. In the unlikely event of a subject withdrawing from the study
 1244 before all three tests are completed, only participants with the full complement of neuroimaging and
 1245 both sensory tests with usable data will be counted toward the total sample size.

1246 It is anticipated that each of the six participating LURN sites will recruit about 42 subjects over the
 1247 course of 2 years (or 7 subjects per site for each of the cells in **Table 10** above), for a total of 252
 1248 participants across the entire LURN Research Network. Participants will be compensated for their effort
 1249 in this study.

1250 **4.3.3 Participant Selection**

1251 Only a subset of patients who enrolled in the LURN Observational Cohort Study (Project 1A) with urinary
 1252 urgency (with or without urgency incontinence) will be eligible for the neuroimaging and sensory testing
 1253 study. The inclusion and exclusion criteria are as followed:

1254 **Urgency subjects:**

1255 *Inclusion criteria:*

1256 ALL of the following criteria have to be fulfilled to be eligible:

- 1257 a. Enrollment in the LURN Observational Cohort Study, including collection of samples for
 1258 biomarker analysis.
- 1259 b. Symptoms of urinary urgency, with or without urgency incontinence, usually with frequency and

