1380 **prior to** sensory testing on the same day, since residual effects of QST may interfere with RSfMRI results.
1381 Usually the QST testing equipment will be physically located in a different building from the functional
1382 MRI scanner.

1383 **Table 11: Schedule of Visits for Neuroimaging & Sensory Testing Case Subjects**

	Observational Protocol Baseline/Initial Visit	Neuroimaging & Sensory Testing Visit
All Components of Baseline/Initial Visit for Observational Protocol (Project 1A) Listed in Table 2, including biosample and DNA collection	X	
fMRI		X
Additional Surveys Listed Above in Section 4.3.4		X
MAST Testing		X
Auditory Stimulation		X

1384

1385 **For control subjects**, they will provide the detailed questionnaire data and the biological specimens in
 1386 the same manner as patients who enrolled in the Observational Cohort Study. Blood, urine, saliva, and
 1387 genital swabs will be collected for storage at the NIDDK Sample Repository for future study by the LURN
 1388 investigators and the broader research community. Preferably, neuroimaging and sensory testing will be
 1389 performed on the same day when the biological specimens and detailed questionnaire data are
 1390 collected. If scheduling conflict or logistic issues does not permit a same day visit when the biological
 1391 specimens and detailed questionnaire data are collected, neuroimaging and sensory testing should be
 1392 performed within a four weeks of that visit (prior to or after).

1393 **Table 12: Schedule of Visits: Neuroimaging and Sensory Testing Control Subjects**

	Screening Assessment (remote)	Neuroimaging & Sensory Testing Visit
Eligibility Assessment	X	
Screening Demographics	X	
LUTS Tool – One Month		X
AUA Symptom Index		X
On-Line Self Report Questionnaires		X
Urine Analysis (dipstick)		X
Pregnancy Test		X
Biosample Collection (Blood, Urine, Saliva)		X
Genital Swab Collection		X
DNA Collection		X
fMRI		X
Additional Surveys Listed Above in Section 4.3.4		X
MAST Testing		X
Auditory Stimulation		X

1394

1395 **4.3.5 Data Collected**

1396 **Resting state functional MRI (RSfMRI):**

1397 *Overview of RSfMRI Data:* Two sets of data (**Urgency RS1 & Empty bladder RS2**) will be obtained from
 1398 each subject. By comparing the “empty bladder” and “urgency” scans within the same subject, we will
 1399 examine the status of the various resting state networks when the bladder is empty versus when the
 1400 subjects reported urgency.

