1506 First, we will report descriptive statistics of the characteristics of the participants. Descriptive statistics
 1507 will include frequencies and percentages for categorical variables, and means, standard deviations, and
 1508 ranges for continuous variables. Variables will also be examined separately by subgroups, such as by
 1509 LURN clinical site sex, race and ethnicity.

1510 **Aim 1**

1511 Aim 1 focuses on examination of RSfMRI and DTI results. We will examine the distribution of
 1512 incontinence severity, diffusivity and anisotropy. Functional connectivity will already be normalized as
 1513 described in section 4.3.4. For ROI pairs of interest, we will use t-tests to compare the mean values of
 1514 the subject-specific correlation estimates among urgency patients and controls. We will use linear
 1515 regression to examine associations of these connectivity measures with incontinence severity, adjusted
 1516 for the subject's age as needed. Additional investigations will use linear regression to control for other

1517 demographic characteristics and potentially confounding variables. Variable inclusion will be guided by a
1518 best subsets approach, with the final model being the one with the highest likelihood score statistic or
1519 explained variance in which all covariates are statistically significant at $p < 0.05$. Multivariable models
1520 will be adjusted for LURN clinical sites whenever appropriate. We will also consider the distribution of
1521 activation levels at each ROI and compare the distribution among subject groups both visually and using
1522 t-tests to test whether mean levels differ between subjects with vs. without a full bladder, between
1523 those with vs. without urinary urgency, and between those with urgency with vs. without incontinence.

1524 Between-groups comparison will also be performed in males and females separately: urgency as a whole
1525 [n=84 each sex] versus control [n=42 each sex].

1526 **Aim 2**

1527 In Aim 2, we will be focused on sensory testing results. We will examine the distribution of sensitivity
1528 thresholds and tolerances. If the thresholds and tolerances are normally distributed or can be
1529 transformed to achieve normality, we will use t-tests to compare the mean values among urgency
1530 patients and controls and Pearson correlations to examine associations with incontinence severity. If the

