1557 Project 1C describes a pilot exploratory study for a potential, larger-scale project aimed at determining
1558 whether the biologic signatures measured by the SomaLogic assay SomaScan can distinguish unique
1559 subtypes of lower urinary tract symptoms (LUTS). The present protocol provides the rationale for the
1560 exploratory biomarker platform, a justification of the “bottom-up” approach for establishing biomarker
1561 signatures, the Specific Aims and Methodologies of the pilot project, and a description of how the
1562 results of the pilot will provide the foundation for a larger-scale biomarker study.

1563 **5.2 Goal of Biomarker Working Group (BWG): A Larger-Scale Biomarker Study**

1564
1565 **The long-term aim of the BWG is to determine biomarkers that can identify**
1566 **unique subgroups of men and women with LUTS.**
1567
1568

1569 LUTS has a negative impact on health-related quality-of-life (HRQoL) and has far-reaching effects on
1570 personal functionality and productivity. Based on a prevalence of 19%, the social costs of symptoms of
1571 lower urinary tract dysfunction (LUTD) have been estimated at nearly \$25 billion per year^[6]. LUTD is
1572 associated with many systemic diseases, e.g. type 2 diabetes mellitus^[7], obesity^[8], and atherosclerosis
1573^[9]. As such, its pathophysiology and response to common medical and surgical therapies is not uniform.

1574
1575 LUTS are prevalent and commonly experienced by both men and women^[10]. Previous research has
1576 identified a multitude of risk factors outside of the genitourinary (GU) system (herein referred to as non-
1577 urologic factors), including depression, anxiety, psychological distress, diabetes, obesity, aging, and
1578 genetic predisposition, which directly contribute to the development and severity of LUTS^[7,8,9,11,12,13].
1579 As such, LUTS have been extraordinarily difficult for researchers to fully characterize. Therefore, the
1580 overarching purpose of the LURN is to carry out deeper phenotyping studies that can ultimately improve
1581 upon the characterization and treatment of men and women with LUTS.

1582
1583 LUTS are difficult for patients to adequately describe and for clinicians to characterize and treat. This is
1584 largely due to the fact that the patient experience of urinary symptoms can be variable and that the
1585 presence and severity of urinary symptoms may be the result of a multitude of pathological processes.

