- 1694 • evaluating the quality of sample collection/storage at each of the six LURN Research
- 1695 Sites

1696 5.4 Materials and Methods

1697 A schematic overview for the pilot project is presented in Figure 6.

1698
1699 **Figure 1: Pilot Biomarker Study Flowchart**

1700

1701 5.5 Participant Selection

1702 For this study, females with LUTS (n=18) and males with LUTS (n=18) that are enrolled in the LURN
1703 Observational Cohort Study will be blindly and randomly selected (3 males and 3 females from each
1704 participating LURN site) from individuals with severe LUTS symptoms (at least one symptom with
1705 severity level 4 or higher, as justified in Section 4.3.3). 24 evaluable controls, (12 females and 12 males),
1706 without LUTS will also be recruited for this study (see Inclusion and Exclusion criteria below). Controls
1707 will be frequency matched with cases by age, sex, race, body mass index (BMI), diabetes status, and
1708 LURN institutional site. Controls should not have significant LUTS, but are not required to be completely

1709 healthy. Exclusion criteria for controls are the same as exclusion criteria for LURN patients, plus the
1710 presence of LUTS. The detailed inclusion and exclusion criteria for controls are presented in Section
1711 4.1.2. Plasma and urine samples for selected cases will be requested from the NIDDK Biorepository. In
1712 order to evaluate SomaScan reproducibility, one female and one male case and one female and one
1713 male control subjects will be randomly selected. For each of these controls, 3 additional aliquots will be
1714 prepared and labeled in a way that does not allow identifying them as duplicates. These blind duplicate
1715 samples will be added to the whole collection of samples (18 female LUTS patients + 18 male LUTS
1716 patients + 12 female controls + 12 male controls + 12 blind duplicates = 72). The total of 72 plasma and
1717 72 urine samples will be analyzed with SomaScan at SomaLogic, Inc. The proposed numbers of cases and
1718 controls in the pilot study are based on literature recommendations^[21, 22, 23, 24] for the sample size in
1719 pilots, which vary from 10-15 per group to 24-36 per group, but are generally not more than 10% of the
1720 planned larger-scale study.

1721
1722 We will record the quality of ongoing biospecimen collections for LURN by obtaining the details
1723 surrounding the specimens being used in this pilot study (e.g., timing of collection, time required to

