1971 n. Botox injection to the bladder or pelvic structures within the preceding 12 months;
1972 o. In men, prostate biopsy within the previous 3 months;
1973 p. In women, pregnancy;
1974 q. History of cystitis caused by tuberculosis, radiation therapy, or Cytoxan/cyclophosphamide
1975 therapy;
1976 r. Augmentation cystoplasty or cystectomy;
1977 s. Presence of urinary tract fistula,
1978 t. Current major psychiatric disorder or other psychiatric or medical issues that would interfere
1979 with study participation (e.g., dementia, psychosis, etc.);

- 1980 u. Inability to relay valid information, actively participate in the study, or provide informed consent
- 1981 (includes uncontrolled psychiatric disease);
- 1982 v. Have received pelvic radiation;
- 1983 w. Have an elevated post-void residual (PVR) urine volume >150 ml;
- 1984 x. Medical expulsion therapy for symptomatic kidney or ureteral stone within 90 days;
- 1985 y. Microscopic hematuria;
- 1986 z. Individual must undergo appropriate evaluation;
- 1987 aa. Positive urinalysis or urine culture;
- 1988 bb. Individual needs to be treated and have a subsequent negative culture, and wait at least 90 days
- 1989 before he or she is eligible;
- 1990 cc. Recent (within 6 months) pregnancy;
- 1991 dd. Breastfeeding.

1992 **5.11.3 Schedule of Visits for Controls**

1993 We will recruit controls without more than minor symptoms (as defined in inclusion criteria above) LUTS
 1994 from the community. Recruitment will be aided by online advertisements (e.g., Craigslist). Controls will
 1995 have a single baseline visit. During this visit, biospecimens will be collected, including whole blood,
 1996 serum, plasma, saliva, genital swabs and urine; controls will also answer LUTS tool and AUA
 1997 questionnaires, as well as the battery of self-reported measures outlined in Section 3.4.7. Plasma and
 1998 urine will be used in this pilot study; the rest of the samples will be kept for future studies.

2000 **Table 15: Schedule of Visits for Biosample Pilot Protocol Control Subjects**

	Initial Visit
Eligibility Assessment	X
Demographics	X
General Clinical Information	X
Clinic Testing (Urine Analysis)	X
LUTS Tool (one month recall period)	X
Self-report Questionnaires, including CASUS LUTS Tool – 1 week recall period AUA Symptom Index	X
Biosample Collection (Whole Blood, Serum, Plasma, Saliva, Urine)	X
Genital Swab Collection	X

- 2001
- 2002 **5.11.4 Urine Collection for Controls**

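### Table 12 schedules no medical history, comorbidity index or height and weight for Project 1B controls, so the planned confounder adjustment of the imaging comparison has no scheduled control-side vascular or metabolic measure

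*Protocol*

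**What the plan says.** **Cases.** Table 11 gives urgency patients "All Components of Baseline/Initial Visit for Observational Protocol (Project 1A) Listed in Table 2, including biosample and DNA collection". Table 2 has separate rows for general clinical information and physical examination. Section 3.4.7 shows what these contain: medical history, the components of metabolic syndrome, the Functional Comorbidity Index, and height and weight. All are filed as clinical data elements, apart from the self-reported symptom measures.

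**Project 1B controls.** Section 4.3.4 says that "they will provide the detailed questionnaire data and the biological specimens in" the same manner as cohort patients. The parity it promises covers questionnaires and specimens. In Table 12 the nearest entry to clinical data is "Screening Demographics", taken at a remote screening contact. No row covers history, comorbidity or physical examination.

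**Project 1C controls.** Table 15 has a row for "General Clinical Information", and Section 5.5 says these controls "will be frequency matched with cases by age, sex, race, body mass index (BMI), diabetes status, and" site.

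**Confounding in Project 1B.** Section 4.3.2 names age as a possible confounder and gives as its example that white-matter "hyperintensities caused by chronic vascular conditions in older subjects may complicate DTI" interpretation. It responds with age matching within sex and two age strata. Section 4.3.7 plans linear regression on "demographic characteristics and potentially confounding variables. Variable inclusion will be guided by a" best-subsets procedure.

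**The concern.** Vascular and metabolic conditions could produce a group difference in imaging by two links, and the protocol contains both. On the imaging side, Section 4.3.2 ties chronic vascular conditions to DTI findings. On the symptom side, Hypothesis 1d(e)-(f) of Project 1A expects more severe urinary symptoms with diabetes, higher BMI, hypertension and hyperlipidemia, and the Project 1B cases come from that cohort. Section 5.2 likewise describes lower urinary tract dysfunction as "associated with many systemic diseases, e.g. type 2 diabetes mellitus", among others.

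The comparison group is volunteers whom Section 4.3.2 describes as healthy, balanced with the cases on sex and age only. If a difference in anisotropy or connectivity appears, the first question will be whether it reflects urgency or the patients' greater burden of vascular and metabolic disease. As scheduled, the study would have the data to answer for the cases but not for the controls. An analysis plan cannot make up for this, because it is a matter of what is collected.

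**Working it through.** **Step 1. Schedules side by side.**

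| Item | 1B cases (Tables 2 and 11) | 1B controls (Table 12) | 1C controls (Table 15) |
|---|---|---|---|
| Demographics | yes | screening only | yes |
| General clinical information | yes | no row | yes |
| Physical examination (height, weight) | yes | no row | no row |
| Self-report questionnaires | yes | yes | yes |
| Biosamples | yes | yes | yes |

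**Step 2. Do the eligibility rules supply the information?** Controls face the Project 1A exclusions, the MRI and sensory-testing exclusions, and a few of their own. These remove overt cerebrovascular and other CNS disease. None excludes hypertension, diabetes, hyperlipidemia or obesity, so passing eligibility does not reveal these conditions.

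**Step 3. Does participation in Project 1A supply it?** Section 6.1.3 says Project 1B requires full participation in Project 1A. Controls cannot meet that, because Section 3.4.4 admits only people with urinary symptoms.

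**Step 4. The plan's own power figure.** Inputs from Section 4.3.6: n = 168 and 84, two-sided alpha 0.05, unadjusted two-sample t-test.

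- Noncentrality = d × √(168 × 84 / 252) = d × √56 = 7.483 d, with 250 degrees of freedom and critical value 1.969.
- d = 0.4, 0.5, 0.6 gives power 0.847, 0.961, 0.994. Table 13 is reproduced.

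**Step 5. Illustration of possible bias.** The documents give no prevalence in controls and no size of shift in an imaging measure, so both inputs are assumptions. The spurious standardised difference is (difference in prevalence) × (shift in SD). With no true urgency effect, the same t-test rejects as follows:

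| Prevalence gap | Shift (SD) | Spurious d | Chance of p < 0.05 |
|---|---|---|---|
| 10 points | 0.3 | 0.03 | 0.056 |
| 20 points | 0.5 | 0.10 | 0.116 |
| 30 points | 0.5 | 0.15 | 0.201 |
| 30 points | 0.7 | 0.21 | 0.347 |

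The middle case, d = 0.10, is a quarter of the smallest effect in Table 13 (0.10 / 0.4 = 0.25).

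Section 3.4.9 uses diabetes as its example of a 10-90 split and BMI of 30 or more as its example of a 30-70 split. If those example splits held among the urgency patients, and no control were affected, the largest possible gaps would be 10 points for diabetes and 30 for obesity. The upper rows of risk are therefore less plausible for diabetes alone than for obesity.

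**The case against.** Several points on the other side have force.

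- **What the protocol names as a confounder.** A reader might infer that it names vascular and metabolic disease as confounders of Project 1B imaging. It does not. Section 4.3.2 names age, with chronic vascular conditions in older people as the example, and Section 4 does not name metabolic disease as a confounder. The metabolic link comes from the Project 1A hypotheses and Project 1C. This stands.
- **Whether adjustment is impossible.** A reader might also infer that adjustment cannot be done, or that no later work could repair the gap. That goes too far. Section 3.1 lists metabolic risk factors within self-report, Section 3.4.7 lets metabolic syndrome rest partly on self-reported history, and controls complete online questionnaires. They also complete the Complex Medical Symptom Inventory, whose content is not shown. Table 12 is not exhaustive either: the post-void residual limit and the medication check have no rows. Yet none of the instruments listed is described as recording these conditions, and Section 3.4.7 files them under history. What is established is that collection is not scheduled, not that it could never happen.
- **Existing protection.** Age matching and the cerebrovascular and CNS exclusions remove part of the vascular imbalance. They do not balance hypertension, diabetes or obesity within an age stratum.
- **Mechanism or confounder.** Section 4.1.1 treats white-matter damage as a possible contributor to urgency. If vascular disease acts through it, some of the difference is the phenotype the study is looking for, and adjustment could remove it. This stands, and it determines how the adjusted result should be used.
- **Analysis detail.** The choice of covariates can be left to an analysis plan. The collection of control data cannot.

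**Conclusion.** The gap is real and limited in scope. Cases have medical history, a comorbidity index and height and weight; for Project 1B controls none of these is scheduled. The adjustment in Section 4.3.7 therefore lacks a planned control-side measure of chronic vascular or metabolic conditions for the urgency-versus-control RSfMRI and DTI comparisons. Analyses within urgency patients, such as those on incontinence severity, are unaffected.

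The size of any bias cannot be known from the documents. The range of about 0.06 to 0.35 for the false-positive rate rests wholly on assumed gaps of 10 to 30 points and shifts of 0.3 to 0.7 SD, and its lower end is close to nominal. It also treats the whole shift as spurious, which the mechanism in Section 4.1.1 leaves open. The case for acting rests on the low cost of closing the gap and on the alternative explanation that the protocol's own text invites. It does not depend on any one of these figures.

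**What to change.** 1. In the visit column of Table 12, add a general clinical information row, using the Project 1A history form with the Functional Comorbidity Index, and a row for height and weight. If the online questionnaires are meant to capture any of this for controls, say which items.
2. In Section 4.3.7, state that the urgency-versus-control imaging comparisons will also be reported adjusted for hypertension, diabetes and BMI, beside the unadjusted result and as a sensitivity analysis. The adjusted estimate should not replace the unadjusted one, because part of what it removes may lie on the pathway to urgency.
3. Section 4.4 has enrolment starting in September 2015 and this version is dated June 2016, so some controls may already have been tested. Sites hold the list linking study numbers to people (Section 6.1.2), and could ask those controls for the history, where consent and ethics approval allow.

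The cost is one existing form and two measurements at a visit the control already attends, a table edit, a few degrees of freedom in the model, and slightly lower precision in the adjusted estimate if the groups differ on these covariates.

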1664 study involved only 35 patients with inflammatory bowel disease. The authors determined the gene
1665 expression profiles of patients and blindly binned them into different subgroups based upon their
1666 expression levels using unsupervised clustering techniques. After the biomarker groups were
1667 determined, the biomarker phenotypes were compared with clinical outcomes. Interestingly, the
1668 clusters were able to predict clinical outcomes. Taken together, these studies demonstrate how a
1669 “biomarker-driven approach” can be used to define clinical phenotypes.

1670 5.3 Rationale

1671 Before embarking upon a large-scale project, several questions and concerns need to be answered. For
1672 example, it is currently unknown whether SomaScan can be used to measure proteins that are relevant
1673 to LUTS. As such, it is important to determine if there are differences in the concentrations of proteins in
1674 patients with LUTS compared with those without LUTS symptoms.

1675
1676 While previous studies have identified proteins contained within plasma and urine that are associated
1677 with the presence and severity of LUTS, the ideal biologic specimen for this purpose remains unknown.
1678 Therefore, it would be prudent to determine the best biospecimen medium (plasma vs. urine) that will
1679 provide the most robust results.

1680
1681 Finally, while biospecimens have been collected as part of the LURN Observational Cohort, before a
1682 large-scale study is performed it will be important to verify if the samples were appropriately collected
1683 by Research Sites for SomaScan assay.

1684 Although SomaScan was used in multiple biomarker studies of complex common diseases, it has not
1685 been applied towards patients with LUTS. Therefore, prior to using this methodology in a large-scale
1686 study, we will perform a pilot project, to inform the design of a future study. In this pilot study, we plan
1687 to assess the feasibility of conducting a larger-scale study by:

[figure not shown]
- 1688 • determining the ideal media for measuring proteins related to LUTS (plasma, urine, or
1689 both)

- 1690 • estimating the number and effect size of biomarkers in a LUTS signature group
- 1691 • estimating covariance matrices of SomaScan targets in LUTS patients and in controls
- 1692 • evaluating the reproducibility of SomaScan assay by using blind duplicates of the
- 1693 samples

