1724 place at -80 degrees, etc.). Only samples that have been processed within 2 hours from collection will be
1725 used for this study. We will send the biospecimens to SomaLogic for analysis on the SomaScan. The
1726 SomaScan will be used to analyze a protein panel of 1310 proteins contained within the plasma and
1727 urine. Results will be sent directly to the LURN data coordinating center (DCC). Data derived from
1728 plasma and urine will be handled independently.

1729 **5.6 Methodology**

1730 **5.6.1 Evaluation of reproducibility of SomaScan**

1731 We will evaluate the reproducibility (measurement error) of a SomaScan assay by performing it on blind
1732 replicates of plasma and urine samples from two different control subjects and two different LUTS
1733 subjects. We will randomly select male and female cases and controls and will send for blinded analysis
1734 the original sample, plus three additional aliquots for each of these subjects. If possible, we will send
1735 these in different batches to include both intra- and inter-assay variability in the assessment of
1736 reproducibility. The presence of four replicates for each of the two cases and two controls will enable us
1737 to estimate the standard deviation, mean, and coefficient of variation (CV) for both controls for each of
1738 the 1310 biomarkers. These CV estimates will be compared with the distribution of CV levels across the
1739 biomarkers (median 4.6%, interquartile range 3.9% to 7.3%) advertised by SomaLogic and provided in
1740 their SOMAscan™ Proteomic Assay Technical White Paper available online
1741 (<http://www.somallogic.com/Technology/SOMAscan-basic-info.aspx>).
1742

1743 **5.6.2 Evaluation of the quality of sample collection/storage**

1744 Strict adherence to the sample collection and storage procedure (for plasma not more than 2 hours
1745 from hand to -80 refrigerator) is crucial for the success of SomaScan assay. Output of the SomaScan
1746 assay is a 1310-dimensional vector with each dimension characterizing abundance of one of 1310 target
1747 proteins in a given patient sample. Length of this vector:

$$L_i = \sqrt{\sum_{j=1}^{1310} A_{ij}^2}$$

1748 (i-subject index, j-protein index, A_{ij} -abundance of protein “j” in the sample of patient “i”)
1749 represents overall protein abundance for each patient sample. If L_i is substantially smaller for the patient

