1750 sample from one of the sites relative to other sites, it could mean that samples at this site were not

1751 collected/stored properly. Sample collection and storage at this site will be reexamined and
1752 recommendations will be provided to study coordinators.

1753

1754 **5.6.3 Estimation of the number and effect size of potential biomarkers; Pathway analysis;** 1755 **Covariance matrices for cases and controls**

1756 The relative abundances of the majority of the proteins in biological systems are not ‘fine-tuned’ and
1757 can vary both in time for a given control and across controls. However, it has been suggested that the
1758 relative abundances of potential biomarkers of LUTS are different in cases compared with controls to a
1759 larger extent than the natural biological variability. It is typical in proteomics studies to consider proteins
1760 differentially abundant when abundance differs by more than 30% from the mean normal value for the
1761 given protein ^[25]. Therefore, we will first estimate the number of differentially abundant proteins by
1762 comparing protein concentrations in cases versus matched controls. Counting all differentially abundant
1763 proteins in the above case-control pairs will provide us with the upper estimate of the number of
1764 potential biomarkers. We will then calculate mean abundances of each protein in cases and controls
1765 separately. Comparison of the mean abundances of the proteins in all cases versus all controls will
1766 provide us with the lower estimate of the number of differentially abundant proteins (potential
1767 biomarkers). Comparison of the difference of the mean protein abundances in cases and controls with
1768 the standard deviation of the abundances of this protein in the controls (measure of natural variability)
1769 will provide the rough estimate of the effect size of the potential candidate biomarker.

1770

1771 Lists of potential candidate biomarkers generated as described above will be submitted into the
1772 pathway analysis software, MetaCore (Thomson Reuters) and geneXplain (geneXplain), for enrichment
1773 analysis to determine the most affected pathways in LUTS cases versus controls. Pathway analysis will
1774 provide us with the information on whether the potential candidate biomarkers are independent or
1775 likely regulated by several common master regulators. We will also calculate covariance matrices for

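### The biomarker pilot judges site sample handling only on samples that already met the 2-hour rule, so it cannot show how often each site misses that rule

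*Protocol*

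**What the plan says.** Section 5.3 explains why the pilot is needed. Specimens have already been banked in the Observational Cohort, and before a "large-scale study is performed it will be important to verify if the samples were appropriately collected" by the sites for the SomaScan assay. One of the five feasibility objectives listed there is "evaluating the quality of sample collection/storage at each of the six LURN Research" Sites.

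Section 5.5 draws 3 men and 3 women with severe symptoms at random from each site and requests their samples from the repository. It then says "We will record the quality of ongoing biospecimen collections for LURN by obtaining the details" "surrounding the specimens being used in this pilot study (e.g., timing of collection, time required to" reach -80 degrees, and so on). The next sentence sets the admission rule: "Only samples that have been processed within 2 hours from collection will be" used.

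Section 5.6.2 gives the standard: "Strict adherence to the sample collection and storage procedure (for plasma not more than 2 hours" from hand to the -80 freezer), and calls adherence crucial for the assay. The site check itself is the vector length L_i, which "represents overall protein abundance for each patient sample. If L_i is substantially smaller for the patient" samples of one site than elsewhere, this may mean that samples there were not "collected/stored properly. Sample collection and storage at this site will be reexamined and" recommendations made. Section 5.6.5 uses the site-quality result in deciding whether the larger study is feasible.

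**The concern.** The samples that enter the site evaluation are chosen on the one handling attribute to which the protocol gives a numerical limit. Whatever share of a site's banked samples was processed late, none of them is assayed. Their handling details are not among those Section 5.5 says will be obtained, and they cannot lower the site's L_i. A site that is usually late and a site that is always on time would look alike on timing.

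Two things are at stake. Section 5.3 asks whether the cohort samples already banked were properly collected, and for timing that question would go unanswered. The feasibility conclusion in Section 5.6.5 would also be drawn without knowing how many banked samples per site meet the rule that the larger study would presumably need.

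**Working it through.** **The plan's own figures.** Samples per medium: 18 + 18 cases, 12 + 12 controls, and 4 subjects × 3 extra aliquots = 12 blind duplicates, total 72. This matches Section 5.5. Cases: 6 sites × (3 + 3) = 36, which also matches.

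**What the filter removes.** Let q be a site's true late rate, which the documents do not give. With the filter, the expected number of late samples among the site's 6 cases is 0 for every q. If the 6 were taken without regard to timing, the expected number would be 6q and P(at least one late) = 1 − (1 − q)^6:

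| q | expected late of 6 | P(at least one late) |
|---|---|---|
| 0.1 | 0.6 | 0.47 |
| 0.3 | 1.8 | 0.88 |
| 0.5 | 3.0 | 0.98 |

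**Could a mostly late site still fill its quota?** Inputs: at least 500 men and 500 women (Section 3.4.9), and 60% of men and 74% of women meeting the severity threshold (Section 5.11.1). Assumptions: an even split over six sites and independent lateness.

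- Eligible men per site: 500/6 × 0.60 = 50
- Eligible women per site: 500/6 × 0.74 ≈ 62
- P(fill) = P(X ≥ 3 | n men, 1 − q) × P(Y ≥ 3 | n women, 1 − q), both binomial

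Example at q = 0.9: for men, 1 − P(X ≤ 2 | 50, 0.1) ≈ 0.888. For women, 1 − P(Y ≤ 2 | 62, 0.1) ≈ 0.955. The product is about 0.85.

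| Late rate q | Full cohort (50 men, 62 women) | Half enrolled (25, 31) | Quarter enrolled (12, 15) |
|---|---|---|---|
| 0.50 | >0.999 | >0.999 | 0.98 |
| 0.70 | >0.999 | 0.99 | 0.65 |
| 0.80 | 0.999 | 0.87 | 0.27 |
| 0.90 | 0.85 | 0.28 | 0.02 |
| 0.95 | 0.28 | 0.03 | 0.001 |

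**Link to feasibility.** Section 5.6.5 cites preliminary simulations with a case cohort of at least 150. If 80% were late at every site, compliant cases above the severity threshold would number about 6 × 112 × 0.2 ≈ 134, yet each site would fill its pilot quota with probability about 0.999. At 75% late the figure is 6 × 112 × 0.25 = 168, and without the severity threshold at 80% late it is 1000 × 0.2 = 200. Supply is therefore not necessarily short, but the pilot as written would not reveal which case applies.

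**The case against.** **Order of steps.** A reader might infer that Section 5.5 first discards every late sample and then draws. The text does not say so. Section 5.11.1 defines the random pool by symptom severity alone, and in Section 5.5 the 2-hour sentence comes after the draw and the repository request. If late samples are found after the draw and replaced, a poor site could reveal itself through replacements. That stands as a limit on what can be claimed. However, the protocol nowhere says that rejections or replacements will be counted by site, so the late rate is missing under either order.

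**What L_i measures.** L_i is an assay result, not a processing time. In samples recorded as on time it can still expose storage failure, thawing or misrecorded times. This stands, and it confines the point to recorded lateness.

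**Two rules.** Section 5.5 speaks of processing within 2 hours, while Section 5.6.2 speaks, for plasma, of reaching the -80 freezer within 2 hours. Some variation in freezer time may therefore remain among admitted samples. This also stands, and the mismatch needs reconciling.

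**Other oversight.** Section 6.6 gives the coordinating center monitoring duties, and Section 8.3 provides for site visits at least yearly with review of source documents. Handling is also governed by a Manual of Operations that is not shown. It would therefore be too strong to say that poorly performing sites get no corrective advice. But the monitoring sections do not mention sample times, and the pilot claims to answer the question itself.

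**Extreme cases.** One might argue that about 6 compliant samples out of 112 (some 5%) would be enough for a site to appear fully compliant. That needs exactly the right split by sex. At 95% late the chance of filling both quotas is only about 0.28, so such a site would usually fall short. The protocol does not treat a shortfall as a quality signal.

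**Conclusion.** The point holds for timing. The plan evaluates site handling on samples selected by the 2-hour rule and obtains handling details only for those specimens, so it cannot estimate how often a site misses the limit it calls crucial. With full enrolment split evenly, a site 70 to 80% late would almost surely supply a full set of compliant cases. The probability drops to about 0.85 at 90% late and 0.28 at 95%, and further with partial enrolment. The late rates, the even split and the enrolment fractions are assumptions.

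It does not follow that any badly run site would pass. The protocol sets no pass mark, L_i may still detect faults other than recorded lateness, and a site with nearly all samples late would often fail to fill its quota. Nor is the 2-hour filter wrong for the protein comparison. The fault is in using the filtered set as the evidence on site handling. The change is worth making because it lets the pilot answer a question it sets itself.

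**What to change.** 1. Keep the 2-hour filter for samples sent to the assay.
2. Before applying it, tabulate by site, from recorded handling times, the distribution of collection-to-freezer times and the share over 2 hours for the banked Project 1A samples. At the least, do this for all samples drawn before filtering, counting rejections and replacements by site.
3. Report this table with L_i in Section 5.6.2, and carry the number of usable samples per site into Section 5.6.5.
4. Describe L_i as a check on compliant samples only.
5. Reconcile the processing wording in Section 5.5 with the freezer wording in Section 5.6.2, so that one definition of the 2-hour limit applies.

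The cost is a little extra tabulation and a wording change, with no new assays, samples or participants. Some sites may show less favourable figures.
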